6.2.8 Day 59 (\pm 7 days)

The following evaluations will be performed at Day 59 (\pm 7 days):

- Physical exam
- Vital signs
- Photograph and measurement of ulcer
- Clinical laboratory tests
- Infection tests
- Tumor markers
- Serum HGF

CONFIDENTIAL

- anti-HGF antibodies
- VM202 DNA levels (If DNA is detected at Day 21)
- Hemodynamic assessments (ABI, TBI, Wave Form)
- Pain VAS
- TcPO₂
- Endothelial progenitor cell assay
- Analgesic Use
- Injection site reaction assessment
- Concomitant medications
- Adverse events

6.2.9 Day 91 (\pm 7 days)

The following evaluations will be performed at Day 91 (\pm 7 days):

- Physical exam
- Vital signs
- Photograph and measurement of ulcer
- Clinical laboratory tests
- Hemodynamic assessments (ABI, TBI, Wave Form)
- TcPO₂
- Pain VAS
- High resolution MRA of lower extremity
- Analgesic use
- Concomitant medications
- Adverse events

6.2.10 Day 180 (± 10 days)

The following evaluations will be performed at Day 180 (\pm 10 days):

- Physical exam
- Vital signs
- Photograph and measurement of ulcer
- Clinical laboratory tests
- Tumor markers
- Anti-HGF antibodies
- Infection tests
- TcPO₂

- Hemodynamic assessments (ABI, TBI, Wave Form)
- Pain VAS
- Analgesic use
- Endothelial progenitor cell assay
- High resolution MRA of lower extremity
- Concomitant medications
- Adverse events

6.2.11 Day 365 (+10 days)

The following evaluations will be performed at Day 365 (\pm 10 days):

- Chest X-ray or CT scan of the chest (if the subject has a previous history of tobacco use, a CT scan will be performed instead of the chest X-ray)
- Physical exam
- Vital signs
- Photograph and measurement of ulcer
- Clinical laboratory tests
- Tumor markers
- Retinal fundoscopy
- Infection tests
- TcPO₂
- Hemodynamic assessments (ABI, TBI, Wave Form)
- Pain VAS
- Analgesic use
- Endothelial progenitor cell assay
- Concomitant medications
- Adverse events

6.2.12 Unscheduled Visits

The data collected during the entire study period are critical for the safety and efficacy assessments, therefore, every effort must be made to bring the subject back to the study site for all visits.

If a subject notifies the site that they have experienced an SAE, or experience an event such as peripheral bypass surgery, peripheral angioplasty or amputation during the follow-up period, they will be encouraged to return to the study site for additional assessments. These events will be reported immediately and the necessary

documentation will be collected. All adverse events that a patient experiences must be reported. The following procedures will be performed for all subjects who have an unscheduled visit:

- Physical exam
- Vital signs
- Anti-HGF antibodies
- Endothelial progenitor cell assay
- Clinical laboratory tests
- Hemodynamic assessments (ABI, TBI, Wave Form)
- Pain VAS
- TcPO₂
- Analgesic Use
- Concomitant medications
- Adverse events

6.2.13 Early Termination Visits

Subjects who have had at least one dose of test material will return to the study site for study specific safety and efficacy assessment visits for the total study period (through Day 365), unless the subject withdraws study consent and refuses to participate. If the subject wishes to withdraw study consent, every effort must be made to encourage the subject to return to the study site for a termination visit assessment prior to withdrawing consent. The following procedures will be performed at the study termination visit:

- Chest X-ray or CT scan of the chest (if the subject has a previous history of tobacco use, a CT scan will be performed instead of the chest X-ray)
- Physical exam
- Vital signs
- Retinal fundoscopy
- Photograph and measurement of ulcer
- Clinical laboratory tests
- Infection tests
- Anti-HGF antibodies
- Endothelial progenitor cell assay
- High resolution MRA
- Hemodynamic assessments (ABI, TBI, Wave Form)
- Pain VAS

- TcPO₂
- Concomitant medications
- Adverse events

If a subject refuses to communicate with the study site, all attempts to contact the subject will be documented. The subject will be sent a certified letter to the subject's last known address.

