This Phase I study is designed to determine the safety and tolerability of intramuscular injections of VM202 using standard objective and subjective measurements. Assessment of safety will be accomplished through monitoring vital signs, monitoring signs and symptoms of acute and chronic hypersensitivity reaction and evaluating all observed and reported adverse events, retinal fundoscopy, clinical laboratory results, tumor lab testing, infection testing and urinalysis. There will also be a long-term follow-up to determine the extent of new onset of malignancy in treated subjects. CA-125 will be done in females and a PSA will be done in males to rule out any occult malignancy prior to first study drug administration and throughout the study.

While the primary objectives are safety and tolerability, preliminary efficacy evaluations will include evaluation of changes from Baseline in hemodynamics (ABI, TBI, Wave Form), TcPO₂, VAS pain assessment, analgesic use, and MRA measurements.

Procedures:

After the study subject is identified, a written informed consent will be obtained and screening process will be initiated. Hemodynamic assessments, TcPO₂, retinal fundoscopy and high resolution MRA will be done at Baseline. For subjects with

ischemic ulcer, a photograph and measurement of the ulcer will be obtained. Safety laboratory (hematology, chemistry, urinalysis), tumor marker tests, infection tests, chest X-ray or CT scan of the chest (if the subject has a previous history of tobacco use, a CT scan will be performed instead of the chest X-ray), and ECG will also be done at Baseline.

Subjects will be administered two doses of study drug on Days 1 and 15 as a local intra-muscular injection in the affected ischemic limb. There will be 4 or 8 injections depending on the dose level administered slowly for 20~30 seconds at predetermined sites on only one affected leg (mainly at the calf muscles) without local anesthesia. After treatment administration, subjects will be observed for 1 hour in a comfortable supine position.

Analgesic usage and Serum HGF will be assessed on Day 8 post first dose treatment.

After the second dose is administered (Day15) to the leg previously injected, hemodynamic assessments (ABI, TBI, Wave Form Analysis), TcPO₂, photograph and measurement of ischemic ulcer, VAS for pain, and safety labs will also be assessed on Days 28, 59, 91, 180 and 365. High resolution MRA with flow assessment will be done at Days 91 and 180.

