Subjects selected for this study will all have critical limb ischemia defined as partial or complete obstruction of a major artery perfusing either the upper or lower extremity that results in pain either at rest or with exertion, numbness, coldness and/or skin ulceration. They may also be a history of prior amputation, dry gangrene or atrophy associated with the above symptoms. Subjects will not be a candidate for either surgical revascularization or angioplasty.

Number of Study Subjects

There will 12-15 subjects selected for participation in this study with 3 subjects treated in each of four (4) study cohorts. There will be an additional 3 patients treated in a cohort if 1/3 subjects experiences a DLT and if the DSMC recommends continuing the trial.

Schedule of Assessments

The schedule of assessments is listed below in Table 4-1.

Table 4-1 Study Procedures Chart	Screen / Baseline		Treatment Period												
		Firs	First Dose Follow-Up Second Dose 2 nd Follow-Up ⁵												
	Day -30 to Day 1	Day 1 pre-dose	Day 1 post-dose	Day 8 (+/- 2days)	Day 15 Pre dose (+/- 3 days)	Day15 Post-dose	Day 16	Day 21 (+/- 3 days)	Day 28 (+/- 3 days)	Day 59 (+/- 7 days)	Day 91 (+/- 7 days)	Day 180 (+/- 10 days)	Day 365 (+/- 10 days)	Unscheduled Visit	Early Termination
Consent Form	X														
Confirm Eligibility		X													
Medical History	X														
Chest X-ray or CT scan of chest ¹	X												X		X
Physical Exam	X				X				X	X	X	X	X	X	X
Vital Signs (HR, BP, Respiratory)	X	X	X	X	X	X	X	X	X	X	X	X	X	X	X
Retinal Fundoscopy	X												X		X
Pregnancy Test	X				X 6										
Photograph and measurement of ulcer	X	X			X				X	X	X	X	X		X
Clinical Lab Tests	X	X			X		X		X	X	X	X	X	X	X
Tumor markers ²	X				X					X		X	X		
Infection tests ³	X									X		X	X		X
Serum HGF		X		X	X			X		X					
anti-HGF antibodies		X			X					X		X		X	X
Blood VM202 DNA		X						X		X^7					
12-lead ECG	X														
High Resolution MRA	X										X	X			X
Hemodynamic Assessment (ABI, TBI,	X	X			X				X	X	X	X	X	X	X
Wave Form)	Λ	Λ			Λ				Λ	Λ	Λ	Λ	Λ	Λ	Λ
Pain VAS	X	X			X				X	X	X	X	X	X	X
Subject Analgesic use	X	X		X	X		X	X	X	X	X	X	X	X	
TcPO ₂	X	X			X				X	X	X	X	X	X	X
Injection site reaction assessment			X	X		X	X	X	X	X					
Mammogram ⁴	X														
Endothelial Progenitor Cell Assay	X		X			X			X	X		X	X	X	X
Concomitant Medications	X	X		X	X		X	X	X	X	X	X	X	X	X
Adverse Events		X	X	X	X	X	X	X	X	X	X	X	X	X	X

CT scan of the chest instead of chest X-ray will be performed if previous tobacco use

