5.4 Subject Withdrawal Criteria

Subjects will be discontinued from the study prematurely if any of the following occur:

- The subject requests to be withdrawn from the study
- The Principal Investigator decides that it is in the subject's best interest

- The subject requires percutaneous or surgical intervention for treatment of acute limb ischemia.
- The subject is noncompliant with the protocol

If a subject withdraws from the study at any time, either at his request or at the Principal Investigator's discretion, the reason(s) for withdrawal will be recorded by the Principal Investigator on the Case Report Form (CRF). If the subject withdraws after receiving any study drug, the subject will be encouraged to continue to be monitored after withdrawal. In this regard, they will be informed that it is in their best interest to return for all follow-up visits to monitor for possible delayed safety effects from the investigational therapy. If possible, all final visit tasks will be completed for all subjects who withdraw from the study. Subjects who withdraw prior to receiving the first dose of study drug will be replaced. Subjects who have received the first dose of the study agent will not be replaced. Subjects withdrawn due to AEs will be monitored until resolution of the AE, as described in Section 8.6.

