6.2.4 Day 15 (± 3 days) Second Study Dose Administration

The second dose of study drug will be administered at Day 15 (\pm 3 days). Prior to the administration of the study agent, the following will be performed:

- Physical exam
- Vital signs (immediately after study drug administration and at 15, 30, and 60 minutes post-dose)
- Photograph and measurement of ulcer
- Urine Pregnancy test (females of childbearing potential)
- Clinical laboratory tests
- Tumor markers
- Serum HGF level

- anti-HGF antibodies
- TcPO₂
- Hemodynamic assessment
- Pain VAS
- Analgesic use
- Concomitant medications
- Adverse events

The study drug will be administered in the same manner and in the same dose as performed on Day 1. Following study drug administration, the following evaluations will be performed:

- Vital signs
- Injection site reaction assessment
- Endothelial progenitor cell assay
- Adverse events
- 6.2.5 Day 16 (post 2nd dosing)

The following procedures will be performed at the Day 16 visit:

- Vital signs
- Adverse events
- Clinical laboratory tests
- Analgesic use
- Injection site reaction assessment
- Concomitant medications
- 6.2.6 Day 21 (\pm 3 days)

The following procedures will be performed at the Day 21 (+ 3 days) visit

- Vital signs
- Serum HGF
- VM202 DNA levels
- Injection site reaction assessment
- Analgesic use
- Concomitant medications
- Adverse events
- 6.2.7 Day 28 (\pm 3 days)

The following evaluations will be performed at Day 28 (\pm 3 days):

- Physical exam
- Vital signs
- Photograph and measurement of ulcer
- Clinical laboratory tests
- Hemodynamic assessments (ABI, TBI, Wave Form)
- Pain VAS
- TcPO₂
- Endothelial progenitor cell assay
- Analgesic use
- Injection site reaction assessment
- Concomitant medications
- Adverse events

After all subjects in Cohort I have completed the Day 28 visit, enrollment will be temporarily suspended until the DSMC has reviewed all of the safety data for all subjects. If the DSMC recommends that the trial continue, enrollment in Cohort II will commence and all of the procedures from Day -30 through Day 28 will be repeated for Cohort II.

After all subjects in Cohort II have completed the Day 28 visit, enrollment will be temporarily suspended until the DSMC has reviewed all of the safety data for all subjects. If the DSMC recommends that the trial continue, enrollment in Cohort III will commence and all of the procedures from Day -30 through Day 28 will be repeated for Cohort III.

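### Tumour markers are the only Day 365 safety test missing from the Early Termination visit, and the required pregnancy test may be up to 30 days old at the first dose

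*Protocol*

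**What the plan says.** **Tumour markers.** Protocol 6.2.11 lists 15 items under "The following evaluations will be performed at Day 365", tumour markers among them. Section 6.2.13 gives its own list under "The following procedures will be performed at the study termination visit", without markers. The Schedule of Assessments section says "The schedule of assessments is listed below in Table 4-1". In that table the marker row is marked at Screening, Day 15 pre-dose, Day 59, Day 180 and Day 365, and is blank under Early Termination. The Day 15 draw comes before dose two: 6.2.4 puts markers under "Prior to the administration of the study agent, the following will be performed".

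The Rationale in the Protocol Synopsis names the safety assessments as including "retinal fundoscopy, clinical laboratory results, tumor lab testing, infection testing and urinalysis". It adds that CA-125 and PSA are used to look for occult malignancy both before dosing and during the study.

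Two clauses bear on subjects who leave. Section 5.4 says "If possible, all final visit tasks will be completed for all subjects who withdraw from the study", and tells dosed subjects that "it is in their best interest to return for all follow-up visits to monitor for possible delayed safety effects". Section 6.2.13 expects dosed subjects to attend through Day 365 unless they withdraw consent and refuse. For those subjects, "every effort must be made to encourage the subject to return to the study site for a termination visit assessment prior to withdrawing consent".

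**Pregnancy test.** Inclusion criterion 7 (5.2) requires a negative serum test before enrolment. Section 6.2.1 allows screening up to 30 days before Day 1. The Day 1 pre-dose list (6.2.2) has no pregnancy test. Section 6.2.4 requires a urine test before the Day 15 dose. Table 4-1 marks only Screening and Day 15 pre-dose.

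**The concern.** Safety is the primary objective, and the product is an angiogenic gene therapy for which the protocol sets up malignancy surveillance. The exit visit keeps chest imaging, fundoscopy, clinical laboratory tests and infection tests but drops the marker panel, and no reason is given. For a dosed subject who withdraws consent and will not return, this is the last chance to draw the sample, and a missed sample cannot be recovered. Dosed subjects are not replaced (5.4, 6.4.2) and each cohort has three subjects, so one such exit removes a third of that cohort's later marker data.

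The pregnancy point is separate. A conception between screening and Day 1 could go undetected at first exposure. The protocol requires a same-day check before dose two but not before dose one.

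**Working it through.** The plan states no figure to reproduce. The check compares lists and then measures the intervals.

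**1. Day 365 (6.2.11) against Early Termination (6.2.13)**

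| Group | Items |
|---|---|
| On both lists (13) | chest X-ray/CT, physical exam, vital signs, ulcer photograph and measurement, clinical laboratory tests, retinal fundoscopy, infection tests, TcPO2, hemodynamic assessments, pain VAS, endothelial progenitor cell assay, concomitant medications, adverse events |
| Day 365 only (2) | tumour markers, analgesic use |
| Early Termination only (2) | anti-HGF antibodies, MRA |

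Count: 15 − 2 = 13 retained. Reading Table 4-1 column by column gives the same two Day 365 items with no Early Termination mark. The Synopsis Rationale and Protocol 7.2.4 class analgesic use as efficacy, so tumour markers are the only safety test dropped.

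**2. Age of the last marker at exit**

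Draws fall on Days 15, 59, 180 and 365. Windows are ±3, ±7, ±10 and ±10 days. The nominal maximum age is the next draw day minus the last one. The maximum with windows takes the latest permitted next draw minus the earliest permitted last draw.

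| Exit between | Nominal maximum | Maximum with windows |
|---|---|---|
| Days 15 and 59 | 59 − 15 = 44 days | (59 + 7) − (15 − 3) = 54 days |
| Days 59 and 180 | 180 − 59 = 121 days | (180 + 10) − (59 − 7) = 138 days |
| Days 180 and 365 | 365 − 180 = 185 days | (365 + 10) − (180 − 10) = 205 days |

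**3. Period with both doses given and no later marker**

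Because the Day 15 draw is pre-dose, this period runs from Day 15 to Day 59. Follow-up is 365 − 1 = 364 days, and 44 / 364 = 12.1%. The segments add up: 14 + 44 + 121 + 185 = 364. The 12% is a share of follow-up time, not a probability that a subject leaves then.

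**4. Pregnancy test**

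Test visits are Screening and Day 15 pre-dose only. Screening may take place on Day 1 or up to 30 days earlier, and assessments outside the window must be repeated (6.2.1). The required test is therefore 0 to 30 days old at the first dose. The Table 4-1 footnote calling for urine tests on the other days adds nothing for Day 1, because Day 15 is the only other marked visit.

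**5. SAP**

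SAP 10.8 lists markers at Screening and Days 59, 180 and 365, omitting Day 15, while SAP Table 22 has a Day 15 row. This is a wording inconsistency only. SAP Table 20 labels fundoscopy by Day 365 and early termination together, so the SAP already expects to use exit values for one safety test.

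**The case against.** The strongest reply is that 5.4 already covers markers. The last scheduled visit is Day 365, so the tasks of a final visit can naturally be read as the 6.2.11 list, which includes them. Most subjects who stop treatment are also expected to keep attending (5.4, 6.2.13, 6.6). This narrows the gap but does not close it. The 5.4 clause is conditional and does not define those tasks. Section 6.2.13 and Table 4-1 give an explicit list without markers, and site staff would follow that list.

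A second reply is that fundoscopy is a weak comparator. It has only one scheduled post-dose assessment, so an early leaver would otherwise have none, whereas markers have four post-baseline draws. That is fair. Infection tests are the better comparator: they are scheduled at Days 59, 180 and 365 and are still kept at exit.

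Third, the consequence is modest. Markers are not a listed primary endpoint and are summarised descriptively in cohorts of three. The interval figures are worst cases, and malignancy surveillance at exit still includes imaging, examination, laboratory tests and adverse events. All of this stands, and it limits the weight of the point.

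On pregnancy, criteria 7 and 8 require contraception or non-childbearing status, and eligibility is confirmed again on Day 1. These make a missed conception unlikely. But reviewing earlier results cannot detect a conception since screening, and the same contraception requirements apply before dose two, where a test is still required. It is also true that the two items are independent and can be decided separately.

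**Conclusion.** Both parts hold. Tumour markers are the only Day 365 safety test absent from the Early Termination visit, and the required pregnancy test can be up to 30 days old at first exposure.

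The marker gap affects only dosed subjects who withdraw consent, attend an exit visit handled by the 6.2.13 list, and do not return. For them the last marker may be up to 44, 121 or 185 days old (54, 138 or 205 with windows). In the 44 days after dose two, about 12% of follow-up, an exit leaves no marker after the full dose. The documents give no withdrawal rate, so the number affected cannot be estimated. It is probably small, and is zero if every dosed subject completes or returns.

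No analysis or inference changes. These are inexpensive improvements to safety data collection that should be made, not errors in the statistical plan.

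**What to change.** - **Protocol 6.2.13 and Table 4-1:** add tumour markers (AFP, CEA, CA19-9, PSA for males, CA125 for females) to the exit list and mark them in the Early Termination column.
- **Protocol 6.2.2 and Table 4-1:** add a urine pregnancy test for females of childbearing potential, negative before dosing, to the Day 1 pre-dose list and column.
- **SAP Table 22:** show Early Termination as its own row with the study day, not pooled with Day 365, because exit times will vary. The programmer note already provides for all available time points, so this is a small clarification.
- **SAP 10.8:** list Day 15 pre-dose and Early Termination among the marker time points.

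The cost is one tube at a visit where blood is already drawn, and one urine test on a day when urine is already collected for urinalysis. The wording changes touch two protocol sections, Table 4-1 and two places in the SAP. There is a small assay cost, and a raised marker at exit may call for follow-up in a subject who is leaving the study.

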6.3 Autopsy

In the event of the death of the study subject, the investigator will be required to request an autopsy from the family of the deceased. An autopsy will assist ViroMed in learning more about the safety and efficacy of gene transfer. If an autopsy is performed, the final autopsy report will be included in the subject's study file and a copy of the report will be sent to both ViroMed and the designated Clinical Research Organization (CRO). The refusal of the family to permit an autopsy will be documented in the study subject's file and on the CRF.

6.4 Concomitant Medications/Treatments

6.4.1 Concomitant Medications

All concomitant medications will be recorded on the CRF at each study visit. There are no prohibited concomitant medications except for other investigational products.

6.4.2 Replacement of Study Subjects

Subjects requiring percutaneous or surgical intervention for treatment of limb ischemia will be withdrawn from treatment. If the subject has received at least the first dose of study drug, the subject will not be replaced. If the subject has received one or both doses of study drug, the subject will remain in the study through the five year follow-up period.

6.4.3 Wound Care

Standard wound care techniques are acceptable (e.g., approved dressings, debridement). No un-approved pharmacological wound care therapies or experimental research materials may be used to treat the wounds during the study observation period. The application of approved growth factors or engineered skin replacements (e.g. Dermagraft®) is permitted. Patients who require hyperbaric treatment as part of their standard of care will be permitted to participate in the study.

6.4.4 Peripheral Vascular Procedures

The performance of any peripheral vascular procedures, including, but not limited to, peripheral bypass surgery, peripheral endarterectomy, peripheral angioplasty or amputation, are events that may occur during the course of the study. The Investigator will document all peripheral vascular interventions performed during the study period.

If the subject reports the occurrence of any disease-related events (e.g., amputation, revascularization bypass, angioplasty), every effort must be made to bring the subject back to the study site for full documentation of the event including sufficient information from the subject, hospital, any treating physician for each peripheral vascular procedure. This information is required by the Sponsor and will be added to the SAE CRF. Information will include:

- Date of intervention
- Type of intervention (e.g., PTA, peripheral bypass, amputation)
- Surgical location (e.g., iliac, femoro-popliteal, infra-popliteal; amputation: AKA BKA)
- Surgical materials (e.g., PTFE, HUV, Dacron)

